4.2. GENERAL RESEARCH METHODOLOGY

The research has the following characteristics:

- ❖ Multicentre study
- ❖ Prospective study
- ❖ Uncontrolled study
- ❖ Non-randomised study

4.3. DESCRIPTION DETAILED OF THE EVALUATION AND THE DATA COLLECTED

a. On patient autonomy:

- **Activities of Daily Living (ADL)** (21): Measured at inclusion (information relating to the week preceding the procedure) (questioning of patient, family, nursing home staff), on day 5 post-op (or on discharge from hospital if discharged before day 5) (*in hospital*), 1 month, 3 months and 6 months post-op (*telephone call*).

Validated scale for assessing independence in simple activities of daily living: hygiene, dressing, mobility, going to the toilet, continence, eating. Each item is coded as follows:

1: done independently

0.5: done partially or with assistance

0: not done

Scale ranging from 0 to 6, with a high score indicating a more independent patient.

- Lawton's 4-item **Instrumental Activities of Daily Living (IADL)** (22): Measured at inclusion (information relating to the week preceding the intervention) (questioning of patient, family, nursing home staff), at 1 month, 3 months and 6 months post-operatively (*telephone call*).

Validated scale for assessing patient autonomy in so-called "instrumental" activities of daily living: managing finances, preparing medication, using the telephone, using transport. Each item is coded as follows:

1 : done alone

0.5: does partially or with assistance

0: does not do

The score ranges from 0 to 8. A high score indicates that the patient is independent. This score can only be interpreted for subjects living at home.

- **Cumulative Ambulation Score** (23): Measured at inclusion (information relating to the week preceding the procedure), from D1 to D3 post-operative, on D5 post-operative (or on discharge if before D5) (*in-hospital*), and at 1 month, 3 months and 6 months (*telephone call*)

Validated score predictive of mortality, morbidity and rehabilitation. Three areas (transfer from lying to sitting, transfer from sitting to standing, walking with appropriate aids) are assessed from 0 (unable despite the help of two people) to 2 (able to do independently). The scores are cumulative over the first 3 days post-operatively and give a score of 0 to 18. A cumulative score greater than 10 corresponds to a 99% probability that the patient will be alive at one month, 93% that they will have returned home, and 94% that they will not have had any major post-operative complications.

b. On the patient's physical performance:

- Measurement of **grip strength** (Hand Grip) on day 5 post-operatively (or on discharge from hospital if this occurs before day 5) (*in-hospital*).

This is measured using a dynamometer. Patients, in a lying or sitting position, are encouraged to squeeze as hard as they can. The best value from three attempts with the dominant hand is used for analysis. The assessment of grip strength using a suitable dynamometer has shown good reproducibility and validity for elderly hospitalised subjects (24).

c. Regarding the surgical procedure:

- **Time to surgery** (time between admission to the emergency department or admission to the ward prior to surgery and the surgical procedure)

- **Types of fractures:**

- * Intracapsular fracture (or true cervical fracture): Garden classification I to IV

- * Extracapsular (or per-trochanteric) fracture: true trochanteric or trochanteric-diaphyseal

- **Surgical procedures:**

- * total or intermediate hip replacement arthroplasty, with or without cement

- * Osteosynthesis

-

- Spinal regional **anaesthesia** or general anaesthesia

- Need for intraoperative or immediate postoperative **transfusion** (recovery room)

- Authorisation for weight-bearing** (surgical instructions)

- Record of transfusions** and the number of red blood cell concentrates administered (intraoperative and perioperative – in the recovery room).

d. Regarding hospitalisation and complications:

- **Length of hospitalisation**

- Occurrence of **acute postoperative confusion** - daily and up to day 10 if the patient is still hospitalised (screened during hospitalisation using the Confusion Assessment Method CAM scale)(26,27).

This is a diagnostic aid, which can be carried out by a nurse, looking for the presence of sudden and fluctuating symptoms, inattention, disorganised thinking and/or disturbances of consciousness. The presence of the first two criteria and the third or fourth criterion leads to a diagnosis of acute confusional syndrome.

During hospitalisation:

- Occurrence of a **post-operative infection** (surgical site, pulmonary, urinary, skin, other) requiring antibiotic therapy.

- Occurrence of **acute urinary retention** requiring urinary catheterisation

- Occurrence of **dislocation/loosening of prosthesis**

- Screening for **iron deficiency** (ferritin < 30 µg/L, CRP > 20 mg/L associated with a transferrin saturation coefficient < 15%) or **vitamin deficiency** (vitamin B12 < laboratory threshold and B9 (folate) < 3.5 ng/mL)

- **Record of transfusions** and number of red blood cell concentrates administered.

- Occurrence of **cardiovascular complications**: deep vein thrombosis, pulmonary embolism, myocardial ischaemia (increased troponin).

- Occurrence of a **neurological complication**: stroke, cerebrovascular accident, etc.

- **Post-operative bleeding** (including localised bleeding and gastrointestinal bleeding)

- Need for **repeat surgery**

- Occurrence of **haematomas**

- **Record of falls**

- **Vital status**

Post-operative M1, M3 and M6:

- Occurrence of **infection** (surgical site, pulmonary, urinary, skin, other), requiring antibiotic therapy.
- Occurrence of **acute urinary retention** requiring urinary catheterisation
- Occurrence of **dislocation/loosening of prosthesis**
- Occurrence of a **cardiovascular complication**: deep vein thrombosis, pulmonary embolism, myocardial ischaemia (increased troponin)
- Occurrence of a **neurological complication**: stroke, etc.
- Need for **repeat surgery**
-
- Record of recurrent **falls or fractures**
- Record of **new hospitalisations** and reasons
- **Vital status**

e. On geriatric assessment

- **CIRS-G(28) scale (in-hospital - inclusion):**

This is a comorbidity scale frequently used in studies because it provides a description of the health status of a population, describing chronic conditions and diseases that have an impact on autonomy, with good reliability and reproducibility

(29). For 14 major systems or groups of systems (cardiac, vascular, pulmonary pathologies, etc.), a score out of 4 is given: 1 being a mild pathology (chronic sinusitis or smoking less than 20 pack-years, for example), 4 is a severe condition causing disability or requiring immediate treatment (acute urinary retention or stroke with hemiparesis).

- **ASA score (30) (in-hospital - inclusion)**

Scale used in anaesthesiology Classifying patients into 6 categories: 1: healthy patient,

2 : with moderate impairment of a major function,

3 : patient with severe impairment of a major function that does not result in disability,

4 : patient with severe impairment of a major function, which is disabling and life-threatening,

5 : moribund patient,

6 : patient declared brain dead whose organs are being harvested for transplantation.

- Screening for depressive symptoms: **MiniGDS** score (*intra-hospital – inclusion*).

- Screening for previous and current **higher function disorders** by interviewing family and friends or consulting the patient's file (*in-hospital – inclusion and during hospitalisation*).

- Screening for **major sensory disorders (in-hospital – inclusion)**.

- **Number of medications** (by class) taken by the patient at inclusion and at the end of hospitalisation, including anticoagulant therapy, antiplatelet therapy, NSAIDs, anti-osteoporotic therapy, analgesics, and at 6 months post-operatively, including anti-osteoporotic and analgesic therapy.

- Patient's **living arrangements (in hospital – inclusion and at 1, 3 and 6 months)**: alone, with family or partner, widowed, in a care home. Home help for shopping, cleaning and personal care.

- **Patient discharge arrangements (in-hospital – end of hospitalisation)**: return home, return to care facility, transfer to follow-up care unit.

- **Previous osteoporotic fractures (in-hospital – inclusion)**: low-energy fractures of the hip, wrist, vertebral body or humerus.

- **Albumin** level (*assessment upon admission, coupled with CRP*): a level below 35g/L upon admission indicates protein-energy malnutrition.

- **Recurrence of falls or fractures** at 1 month, 3 months and 6 months post-operatively (*telephone call*).

4.4. SPECIAL SITUATIONS

Dementia patients: the interview with dementia patients will be completed by their family or nursing home staff. Information about participation in the study will be provided to the family/trusted relative.

If surgery is postponed (due to the patient's general condition or the presence of antiplatelet or anticoagulant treatment, for example), D0 remains the date of the procedure and corresponds to the patient's return to the orthopaedic/orthopaedic surgery department (after the procedure).

If the patient is discharged early, a standardised prescription will allow haemoglobin to be monitored on D5, D10 and D15 (timeframe: +/- 2 days).

A patient may receive a transfusion,

- pre- or peri-operative transfusion in the recovery room
- post-operative transfusion
 - In hospital: during the orthopaedic stay
 - Post-hospital: new hospitalisation required for transfusion

4.5. REASON FOR THE TELEPHONE CALL

This study is aimed at elderly and often frail patients. The participating centres are referral centres that treat patients from all regions. For the most optimal and objective recovery possible, the 1-month, 3-month and 6-month assessments should have taken place during a geriatric consultation. Due to the likely frailty of the patients, the absence of systematic post-hospitalisation surgical consultations, and the sometimes significant distance from the patients' place of residence, we felt it was reasonable to limit this follow-up to a telephone follow-up, either with the patient, their family or the nursing staff at the nursing home. Thus, the telephone assessments are based on simple criteria that can be assessed over the phone.

It should be noted that follow-up, including autonomy, was also carried out by telephone during the study by Halm et al. (19).

4.6. IDENTIFICATION OF ALL SOURCE DATA NOT INCLUDED IN THE MEDICAL RECORD

- Lifestyle and living environment
- Previous fractures
- Screening for previous or current higher brain function disorders
- Screening for major sensory disorders
- Screening for depressive symptoms (mini GDS)
- Handgrip strength measurement
- ASA/CIRS-G/CAS/ADL/IADL score
- Screening for confusion (CAM)
- Discharge mode
- Late post-operative complications
- Recurrence of falls or fractures

4.7. RULES FOR DISCONTINUING A PERSON'S PARTICIPATION

4.7.1. Criteria for premature termination of a person's participation in the research

Any patient included in the protocol who no longer wishes to participate will be withdrawn from the study as soon as they express their request.

4.7.2. Procedures for discontinuation of participation of a person in the research

For the terms and conditions governing the use of data from individuals who have withdrawn prematurely from the study, please refer to the statistics section.

4.7.3. Criteria for discontinuing part or all of the research (excluding biostatistical considerations)

Part or all of the study may be terminated permanently or temporarily by decision of the French National Agency for Medicines and Health Products Safety (ANSM), the CPP, or the study sponsor.

In all cases:

- Written confirmation will be sent to the study's coordinating investigator (specifying the reasons for early termination).
- All patients in the study will be informed and will be required to attend their early exit visit.

To complete this section, refer to the "statistics" section, which presents the statistical criteria for stopping the research.

5. DATA MANAGEMENT AND STATISTICS

5.1. *COLLECTION AND PROCESSING OF STUDY DATA*

5.1.1. *Data collection*

An electronic case report form (eCRF) will be created for each patient. All information required by the protocol must be provided in the eCRF. It must include the data necessary to confirm compliance with the protocol and all data necessary for statistical analysis; it must allow for the detection of major deviations from the protocol.

The person(s) responsible for completing the eCRF (investigator, ARC, etc.) must be defined and identified in the table of delegated responsibilities for each centre (kept in the investigator's binder).

5.1.2. *Data coding*

By signing this protocol, the principal investigator and all co-investigators undertake to keep the identities of the patients who participated in the study confidential.

Each patient included in the study will be assigned an incremental code consisting of the following three items: treatment centre number, serial number, initials (first letter of surname and first letter of first name).

This code will be the only information that will appear on the electronic case report form (eCRF) and will enable the eCRF to be linked to the patient at a later date.

The investigator is also required to code patient data on all documents in their possession (imaging reports, biology reports, etc.) that are attached to the eCRF.

5.1.3. *Data processing*

Clinical data collection will be based on the establishment of a database and the creation of data entry forms modelled on the observation log, in accordance with the protocol and regulations currently in force.

5.2. STATISTICS

Statistical analyses will be performed by [name], Statistical Engineer at the Vendée Departmental Hospital Centre.

Statistical analyses will be performed using R software version 3.5.3.

5.2.1. Description of methods planned planned, including the schedule for planned interim analyses

All variables collected will be described by minimum, maximum, quartiles, mean and standard deviation for quantitative variables and by number and percentage of each modality for qualitative variables.

Analysis of the primary endpoint:

The relationship between loss of independence at 6 months and post-operative anaemia will be analysed using a logistic model. If a link is found, a multivariate analysis will be performed to confirm the independence of the anaemia/independence relationship. To do this, all potential confounding factors will be tested in a univariate analysis. Factors associated with a p value <0.20 will be retained in the multivariate model.

Analysis of secondary criteria:

- The analysis of the relationship between loss of autonomy on day 5 (or on discharge from hospital if discharged before day 5), at 1 and 3 months, and post-operative anaemia will be performed using the same method as for the primary endpoint.
- The 6-month mortality rate will be estimated with its 95% confidence interval using the Kaplan-Meier method.

The association between anaemia and mortality at 6 months will be studied using a Cox proportional hazards model in order to take confounding factors into account.

- The progression of post-operative anaemia (D0 to D15) will be described graphically.

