Postoperative anaemia has multiple causes. It is probably aggravated by rehydration upon admission of patients with fractures (7). There is blood loss associated with the fracture and the formation of a haematoma prior to surgery (8), but also some postoperative occult bleeding: in 546 patients with a fracture of the upper end of the femur, Foss et al. showed that post-operative occult bleeding ranged from 547 to 1473 mL, in addition to the blood loss observed during surgery. Finally, there is a degree of acute inflammatory anaemia secondary to surgery. This inflammatory component is caused by a decrease in progenitor proliferation, a reduced red blood cell half-life and iron retention by macrophages. This retention is mediated by ferritin, which is then increased, and by hepcidin, a recently discovered protein that regulates iron metabolism (9).

Loss of independence, defined as a decrease in the ability to care for oneself, is also significant after a fracture of the upper end of the femur. Of 390 patients over the age of 65 who underwent surgery for an FESF and were analysed by Vochteloos team, nearly half did not regain their previous independence after one year. Only 25% of patients who were mobile without assistance regained their previous independence within three months of surgery. Nineteen percent of patients became bedridden. The most significant risk factors were a low level of previous independence and the occurrence of postoperative confusion (10).

The consequences of a loss of independence in elderly people are manifold (11). It leads to the intervention of outside help for activities of daily living, a change of living arrangements, a change in family relationships, and a risk of abuse by carers. The economic consequences are also significant:

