2.1.2. Primary evaluation criterion

- Haemoglobin level on day 5 post-operatively (considered the post-operative haemoglobin reference level in this study)
 - In the case of patients who received a transfusion postoperatively, the reference haemoglobin level will be the haemoglobin level at the end of hospitalisation
- Change in the Activities of Daily Living (ADL) score pre-fracture and 6 months post-operatively.
A loss of independence will be defined as a decrease of one point or more in the ADL.

The reference value for haemoglobin levels was arbitrarily set at 5 days post-operatively. This is because haemoglobin levels recorded in A&E or on admission to the ward prior to surgery, or immediately post-operatively, may be influenced by factors other than isolated anaemia. Dehydration, present in the emergency department or on admission to the ward before the operation, corrected preoperatively, and postoperative haemodilution due to fluid replacement, cause the haemoglobin level to vary without there being any real deglobulation. We therefore postulate that the haemoglobin level on the 5th postoperative day can serve as a reference.

Confounding factors collected

All confounding factors related to loss of autonomy will be collected:

- Transfusion and number of red blood cell concentrates received

The indication for transfusion is at the discretion of the prescriber. However, it is generally accepted to transfuse patients with haemoglobin levels below 8 g/dL, or below 10 g/dL in cases of ischaemic heart disease or poor clinical tolerance.

- Age
- Gender
- Height, weight, Body Mass Index (BMI) calculation
- Screening for past or present higher brain function disorders
- Screening for major sensory disorders
- Screening for depressive symptoms: Mini Geriatric Depression Scale (MiniGDS)
- Comorbidities assessed using the Cumulative Illness Rating Scale - Geriatrics (CIRS-G)
- ASA score
- Number of medications (per class) taken by the patient (anticoagulants, antiplatelet agents, NSAIDs, anti-osteoporotic drugs, analgesics)

- Lifestyle and living environment
- Severe fractures before and after inclusion
- Other falls during the year
- Protein-energy malnutrition
- Iron deficiency (ferritin < 30 µg/L or CRP > 20 mg/L associated with a transferrin saturation coefficient < 15%)
- Recurrence of falls at 1, 3 and 6 months post-op

2.2. *SECONDARY OBJECTIVES AND EVALUATION CRITERIA*

2.2.1. *Secondary objectives*

The secondary objectives are to analyse:

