5.2.3. Expected degree of statistical significance

The significance threshold is set at 5%.

5.2.4. Method of unused or invalid data into account of missing,

No imputation will be performed on missing data. These will be described in terms of numbers and percentages.

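### The adjusted model for loss of independence runs only if the crude model shows a link; its covariates are not fixed, pre-fracture ADL is not guaranteed, and later falls and fractures are candidates

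*Combined protocol and SAP*

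**What the plan says.** Section 5.2.1 fits a crude logistic model of loss of independence at 6 months on post-operative anaemia. Adjustment follows conditionally: "If a link is found, a multivariate analysis will be performed to confirm the independence of the anaemia/independence relationship". All potential confounders are tested one at a time, and "Factors associated with a p value <0.20 will be retained in the multivariate model". No covariate is forced in. The analyses at day 5, 1 month and 3 months "will be performed using the same method as for the primary endpoint". Mortality has no such gate: it uses a "Cox proportional hazards model in order to take confounding factors into account", with no covariates named. Section 5.2.3 gives a single significance threshold, 5%.

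The only list of confounders is in section 2.1.2. It has 16 bullets. Pre-fracture ADL is not one of them, although sections 4.1 and 4.3 collect it and it forms half of the change score. The list does include severe fractures after inclusion as well as before, and falls at 1, 3 and 6 months.

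The exposure is haemoglobin on day 5. For patients transfused post-operatively, "the reference haemoglobin level will be the haemoglobin level at the end of hospitalisation".

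**The concern.** In an observational study the adjusted estimate and its interval are the answer to the question, whatever the crude result. Here the crude p value decides whether they exist. The criterion for a link is not stated; the 5% threshold is presumably meant.

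Two further features weaken the adjusted model when it does run. First, nothing commits it to baseline function, although section 1.1 describes two cited studies that adjusted for it (the retrospective cohort of 5,793 patients and the prospective study of 550). The change score does not do this job. Loss is a drop of at least one point on a 0–6 scale, so a patient starting at 0 or 0.5 cannot have the event. Second, follow-up falls, and most fractures after inclusion, occur after the reference haemoglobin. They may be consequences of anaemia or of lost independence. Adjusting for them can remove part of the association under study.

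Section 1.2.1 hopes to derive a management protocol, including transfusion strategy, from the results. An absent or poorly adjusted estimate is a weak basis for that.

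**Working it through.** **Plan's own figure.** Section 5.2.2 gives 255 analysable patients from 320, with 10% deaths and 10% lost. 320 × (1 − 0.10 − 0.10) = 256 and 320 × 0.9 × 0.9 = 259, so 255 is reproduced to within rounding.

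**Events and parameters.** Section 5.2.2 cites 67.8% regaining independence and asks for 10 events per factor.
- 255 × (1 − 0.678) = 82 events, about 8 parameters.
- If the cited 6.3% deaths are among the non-recoverers: 255 × (0.322 − 0.063) = 66 events, about 6 parameters.

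The list has 16 bullets. If all were independent noise, the screen would still keep 16 × 0.20 = 3.2 on average.

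**How often the gate stays closed, no confounding.** Assumptions: 65% exposed (section 5.2.2's share below 10 g/dL), true odds ratio 2.0, and event rate 32.2% or 49%. The 49% stands for the cited study in which "nearly half did not regain their previous independence after one year". Both rates are 12-month figures.

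At 32.2%, solving 0.35·p0 + 0.65·p1 = 0.322 with an odds ratio of 2 gives p0 = 0.229 and p1 = 0.372. With 255 × 0.65 = 165.75 exposed and 255 × 0.35 = 89.25 unexposed:
- SE = √[1/(165.75 × 0.372 × 0.628) + 1/(89.25 × 0.229 × 0.771)] = 0.299
- z = ln 2 / 0.299 = 2.32
- P(p ≥ 0.05) = Φ(1.96 − 2.32) = 0.36

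At 49%, p0 = 0.379, p1 = 0.550, SE = 0.268, z = 2.58 and P = Φ(−0.62) = 0.27. Simulation gives the same, 36.1% and 26.8%.

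For larger n, z grows with √(n/255).

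| n (400 and 600 assumed) | Gate closed, formula | Gate closed, simulation |
|---|---|---|
| 255 | 27–36% | 27–36% |
| 400 | 10–17% | about 10–14% |
| 600 | 2–6% | about 2–4% |

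**Adjusted result significant, gate closed.** Simulated at n = 255 with a 5% gate. The masking confounder is assumed to have 30% prevalence and an odds ratio for loss of 0.33–0.5, with anaemia 10–20 percentage points commoner when it is present. A significant adjusted result is hidden in 7–28% of studies. With no confounding, or confounding in the same direction as the effect, the figure is under 1%.

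**Adjusting for falls.** Assume 20–30% fall, anaemia doubles the odds of falling, a fall multiplies the odds of loss by 2–3, and the total odds ratio is 2.0. Within each anaemia group, with fall risk f, loss risk y and fall odds ratio OR_F, solve (1 − f)·expit(a) + f·expit(a + ln OR_F) = y. The adjusted odds ratio is exp(a1 − a0), where 1 is anaemic and 0 is not. At 32.2% events:
- 20% fall, OR_F 2 (f = 0.134 and 0.236): 1.87
- 30% fall, OR_F 3 (f = 0.211 and 0.348): 1.76

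This removes about 9–19% of the log odds ratio.

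**The case against.** Several points on the other side stand.

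- **Pre-fracture ADL is not barred.** Section 5.2.1 tests all potential confounders and does not restrict them to the list in section 2.1.2, so ADL could be admitted. What remains is that nothing commits to it.
- **The gate rarely hides a positive result unless confounding masks the effect.** No listed variable is identified as a masking confounder. A reader might infer that the plan will miss a real association, but the documents give no direction of confounding and do not support that.
- **255 is not the final sample size.** It comes from 18 months at one hospital; the study is multicentre (section 4.2) with 42 months of inclusion (section 4.1). The gate closes less often as n grows.
- **The cited evidence on baseline function concerns walking.** Section 1.1 reports, from the study that also supplies the 49% rate, "The most significant risk factors were a low level of previous independence and the occurrence of postoperative confusion". It then says that the studies cited to that point gave priority to walking. Neither finding is about a one-point ADL loss.

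A reader might also infer that the p<0.20 screen will lose pre-fracture ADL and so badly bias the anaemia estimate. That is not shown. In simulation with 5–10% of patients at ADL 0 or 0.5, and anaemia assumed 20 points commoner at low ADL, leaving ADL out gives an odds ratio of 1.85–2.27 against a true 2.0. The larger distortion, 1.55–1.60, needs 20% at that floor and 49% events, and there the screen almost never drops ADL.

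Finally, using the same method at earlier time points need not mean the same covariates. Month-6 falls entering a day-5 model, or falls entering the Cox model, is possible but not stated.

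**Conclusion.** The point holds, and it should be fixed. The plan makes the adjusted estimate for its primary question conditional on a crude result, leaves its covariates to a univariate screen, does not guarantee a collected baseline score, and lists variables that mostly follow the exposure. These rest on the text alone.

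The sizes are illustrations under assumed effects. At n = 255 and an odds ratio of 2.0, about a quarter to a third of studies would have no planned adjusted estimate, and far fewer at 400 or 600 patients. Most of those would also be non-significant after adjustment, so the usual loss is the adjusted estimate and its interval, not a positive finding. The 7–28% hidden by masking applies only if confounding runs that way. Adjusting for falls attenuates modestly. No claim is made about how large a bias would follow from omitting pre-fracture ADL in this population.

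**What to change.** - Report the adjusted logistic model as the primary analysis whatever the crude p value, with the crude result alongside. Do the same at day 5, 1 month and 3 months.
- Replace the p<0.20 screen with a short covariate set fixed in advance from variables that precede the reference haemoglobin, always including pre-fracture ADL. One example adds age, sex, cognitive disorder and CIRS-G; with haemoglobin as a single term that makes 6 parameters.
- Keep to section 5.2.2's own rule: about 6–8 parameters in total at 66–82 events, and more only if observed events allow. If haemoglobin enters as severity classes, count each extra term.
- Exclude follow-up falls and post-inclusion fractures from the adjustment set, here and in the mortality Cox model. Describe them as outcomes.
- Report results with and without in-hospital transfusion. For patients transfused post-operatively in hospital, it precedes the end-of-hospitalisation reference value.
- Add a sensitivity analysis limited to pre-fracture ADL of at least 1.

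The cost is analysis-plan wording, because every variable is already collected. Fewer listed factors would be adjusted for. Since section 5.2.4 rules out imputation, patients missing a fixed covariate leave the adjusted model, and their number should be reported.
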